6.4 Demographics and Baseline Characteristics

Demographics and baseline variables (described in section 4.2) will be descriptively summarized.

6.5 Other Subject Characteristics

Anti-JC virus antibody test

Anti-JCV antibody test result (positive or negative) is judged according to the results of screen assay and inhibition assay. The results will be descriptively analyzed in the corresponding visit for each of the three analysis periods.

6.6 Study Windows

Week of evaluation for analysis will be defined in table 1 (similar approach as used in the E6011-J081-101 study).

See Table 1 Study Windows below for reference days:

Table 1 Study Windows

Analysis Visit Number	Analysis Visit	Target	Window	
			Lower	Upper
2	Baseline	1	-	-
3	Week 1	8	5	11
4	Week 2	15	12	18
5	Week 4	29	22	35
6	Week 6	43	36	49
7	Week 8	57	50	63
8	Week 10	71	64	77
9	Week 12	85	78	91
10	Week 13	92	-	95
11	Week 14	99	96	102
12	Week 16	113	106	119
13	Week 18	127	120	133
14	Week 20	141	134	147
15	Week 22	155	148	161
16	Week 24	169	162	175
17	Week 28	197	190	203
18	Week 32	225	218	231
19	Week 36	253	246	259
20	Week 40	281	274	287
21	Week 44	309	302	315
22	Week 48	337	330	343
23	Week 52	365	358	371
24*	Week 56	393	386	399
25*	Week 60	421	414	427
26*	Week 64	449	442	455

*Only for non-responders at week 12

The window for the post observational visit (28 days after completion/discontinuation of the treatment):

- For patients that discontinue treatment, the target day will be 28 days after the discontinuation date and the window will be [discontinuation date+1 , 58].
- For patients that complete the extension period or complete the rescue period but because of a lack of efficacy do not continue to the extension period, the target day will be 28 days after end of extension/rescue period date and the window will be [extension/rescue period end date +1 , 58].

Observation that has the most recent date-time on base date-time is adopted if plural observations exist in the time window.

In case that two or more assessments falling in the same window, the closest in absolute value to the target will be chosen. In case of a tie, the earliest assessment will be considered.

Pre-dose pharmacokinetic blood samples should be collected prior to dosing, no time window is advised for this sample. Post dose pharmacokinetic blood samples should be collected within a 10-minute time window starting from the end of the E6011 infusion.

Biomarker/pharmacogenomic samples should be collected during the following time windows specified below;

- During the remission induction period (all subjects), blood samples should be collected within \pm 1 day during Week 1, and within \pm 3 days during Weeks 2 to 12.
- During the extension period (responders), blood samples should be collected within \pm 7 days during Weeks 16 to 52.
- During the rescue period (non-responders), blood samples should be collected within \pm 1 day during Week 13, and within \pm 3 days during Weeks 14 to 24.
- During the extension period (non-responders), blood samples should be collected within \pm 7 days during Weeks 28 to 64.

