# 9.5.2 Observation/assessment items and the study schedule 9.5.2.1 Study schedule

Table 4 shows the schedule for this clinical trial.

Observations and assessments conducted after the start of IMP administration are scheduled beginning from the start date (Day 1) of IMP administration. If observations/assessments need to be rescheduled for whatever reason during the remission-induction period, they must be conducted within plus or minus 1 day of the scheduled date in Week 1 and thereafter plus or minus 3 days of the scheduled dates up to Week 12. During the rescue period, they must be conducted within plus or minus 1 day of the scheduled date in Week 13 and thereafter plus or minus 3 days of the scheduled dates up to Week 24. During the extension period and post-observation period, they must be conducted within plus or minus 7 days of the scheduled dates ("within plus 7 days" of "70 days after the last IMP administration").

Assessments during the follow-up period are to be scheduled using calendar days counting from the date of the last IMP administration. From the last IMP administration to 2 years thereafter, they must be conducted within plus or minus 1 month of the scheduled dates (example: if the last IMP is administered on 1 November 2019, the scheduled date follow-up would be 1 May 2020; the window in this case would be between 1 April 2020 and 1 June 2020).

Date: 18-Apr-2022 version 11.0 Confidential Page 53 of 80

Table 4 E6011-ET2 Study Schedule (All Subjects)

	Screening period		F	Remission	-induction	period (d	ouble-blii	nd)		
Visit	1	2	3	4	5	6	7	8	9	-
Test/Observation Time	Days -42 to -1 days	Week 0 i	Week 1	Week 2	Week 4	Week 6	Week 8	Week 10	Week 12	Disco ntinua tion j
Allowed deviations	1 days	_	± 1 day	± 3 days	_					
Signing of informed consent a	0									
Demographic characteristics, history of present illness	0									
Past medical history, complications	0									
Inclusion/exclusion criteria check	0	0								
Colonoscopy b	0								0	0
IMP administration c		0	0	0	0	0	0	0	○ k	
Prior treatment and	→									→
concomitant drugs/therapies										
Physical findings	0	0	0	0	0	0	0	0	0	0
Height/weight d	0	0		0	0		0		0	0
Vital signs	0	0	0	0	0		0		0	0
Standard 12-lead ECG	0								0	0
Chest X-ray test	0									
Neurological symptoms e	0								0	0
Anti-JCV antibody test	0									0
Blood CD4 + cell test	0								0	0
Viral test, tuberculosis test	0									

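### SAP extension windows stop at target +6 days while the protocol allows +7, so a compliant visit made exactly 7 days late gets the wrong analysis week or none

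*SAP*

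**What the plan says.** Protocol 9.5.2.1 fixes the day count: "Observations and assessments conducted after the start of IMP administration are scheduled beginning from the start date (Day 1) of IMP administration". For the extension it then gives the tolerance: "During the extension period and post-observation period, they must be conducted within plus or minus 7 days of the scheduled dates". The allowed-deviation rows of the schedules in both documents repeat 7 days either side for every extension visit. SAP 6.6 repeats the same tolerance for biomarker samples, for responders from Week 16 to 52 and for non-responders from Week 28 to 64.

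The analysis week is set separately. SAP 6.6 states that "Week of evaluation for analysis will be defined in table 1", the Study Windows table. Its columns are visit, target, lower limit and upper limit. The rows that matter most here are "Week 16 113 106 119", "Week 18 127 120 133", "Week 20 141 134 147", "Week 22 155 148 161" and "Week 52 365 358 371". The Week 64 row has target 449 and limits 442 and 455. One table serves both schedules. Only Weeks 56, 60 and 64 are marked as applying to Week 12 non-responders alone; Weeks 18 and 22 carry no such mark.

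SAP 6.6 says what to do when several assessments fall in one window. It does not say what to do when an assessment falls in none. SAP 6.11 declares no modifications from the protocol's statistical section.

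**The concern.** A visit that the protocol permits should receive the week for which it was scheduled. Here the latest permitted day of every extension visit does not.

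The data exposed are those summarised by visit in the extension: CDAI, PRO2, SES-CD, laboratory values, vital signs and anti-E6011 antibodies. SAP 6.8 includes the entire administration period in the efficacy analysis, and long-term efficacy and safety is a secondary objective. Apart from discontinuation, Week 52 (responders) or Week 64 (non-responders) is the only scheduled extension colonoscopy, so a missed window there can leave a subject without a long-term SES-CD value in the by-visit summary. Protocol 9.7.2 reports 25 enrolled subjects, so one misplaced visit is noticeable in a table.

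**Working it through.** **Inputs.** First IMP day is Day 1, and the extension tolerance is 7 days either side (Protocol 9.5.2.1). Windows are from SAP 6.6, Table 1 (Study Windows). Extension visits are Weeks 16 to 52 every four weeks for responders and Weeks 28 to 64 every four weeks for non-responders.

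**Step 1: reproduce the table.** Target = 7 × week + 1. Week 16: 7 × 16 + 1 = 113. Week 52: 7 × 52 + 1 = 365. Week 64: 7 × 64 + 1 = 449. All 24 post-baseline targets reproduce. Every extension lower limit equals target − 7 (113 − 7 = 106; 365 − 7 = 358; 449 − 7 = 442). No extension upper limit equals target + 7; each equals target + 6 (119, 371, 455).

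**Step 2: try another day count.** Counting from Day 0, Week 52 would be 364, with limits 357 to 371. That matches the upper limit, but not the target (365) or the lower limit (358). A different day origin does not explain the table.

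**Step 3: look up each permitted day.** For all ten visits in each schedule, days −7 to +6 fall in the intended week. Only day +7 does not:

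| Schedule | Visit at +7 | Day | Week assigned |
|---|---|---|---|
| Responders | Week 16 | 113 + 7 = 120 | Week 18 (120–133) |
| Responders | Week 20 | 141 + 7 = 148 | Week 22 (148–161) |
| Responders | Week 24 | 169 + 7 = 176 | none |
| Both | Weeks 28, 32, 36, 40, 44, 48 | 204, 232, 260, 288, 316, 344 | none |
| Both | Week 52 | 365 + 7 = 372 | none |
| Non-responders | Weeks 56, 60 | 400, 428 | none |
| Non-responders | Week 64 | 449 + 7 = 456 | none (after the last window) |

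The post-observation window starts the day after the period end date, so it does not pick up a late Week 52 or Week 64 visit that is itself the period end.

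**Step 4: the blinded and rescue periods.** The Week 12 tolerance is 3 days: 85 − 3 = 82 to 85 + 3 = 88, inside the window 78–91. The even-numbered induction and rescue visits with a 3-day tolerance all map correctly, including non-responder Week 24 (166–172 inside 162–175).

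**Step 5: size.** The documents give no visit timing, so the share of visits at exactly +7 is an assumption. The ten-visit column also assumes independent visits and uses 1 − (1 − share)^10.

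| Assumed timing within ±7 days | Share at +7 | At least one in ten visits |
|---|---|---|
| Even over 15 days | 1/15 = 6.7% | 1 − (14/15)^10 = 49.8% |
| Normal around target, SD 3 days | about 0.9% | about 9% |
| Normal around target, SD 2 days | about 0.05% | about 0.5% |

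**The case against.** The strongest reply is that the exposure is narrow. It is one permitted day in 15 per visit, and the wrong-week label arises on two days only, for responders only. An even spread is an extreme assumption. If visits cluster near target, few or none fall at exactly +7. All of this stands.

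Much of the extension reporting is also untouched. Under SAP 6.9.1 adverse events belong to the period in which they start. SAP 4.8 and 4.10 summarise drug concentrations and biomarkers by nominal time point. SAP 6.9.4 limits the ECG and neurological summaries to the first 12 weeks. This also stands, and it confines the point to the by-visit summaries listed above.

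Three stronger readings are tempting, and the documents do not support them:

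- **The final visits are discarded.** The SAP does not say that unwindowed data are dropped. It gives no rule, which is the supportable criticism.
- **An observed response becomes a failure.** The non-responder rule in SAP 6.8.2 covers missing secondary endpoint data, but it is written around discontinuation before 12 weeks. Whether it carries into the extension, or applies to a visit that took place, is not stated.
- **The 14-day holes between four-weekly windows lose many visits.** In each hole between Day 176 and Day 441 only the first day is a permitted visit day; the other 13 are outside tolerance. The gaps at Days 19–21 and 103–105 contain no permitted day. A discontinuation assessment, which has no scheduled day, could fall in a hole. That is a further reason to state a rule, but it is not part of the mismatch shown here.

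**Conclusion.** The mismatch is real and follows from day arithmetic alone: protocol tolerance ±7, SAP windows −7 to +6, at every extension visit in both schedules. A compliant visit at +7 is put in a week the subject does not have (responder Weeks 16 and 20) or in no week (all later extension visits, including Weeks 52 and 64).

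The size is modest. It concerns by-visit descriptive summaries in an open-label period. Between under 1% and 6.7% of extension visits would be affected under the timing assumptions shown, and the actual number cannot be derived from the documents. The −7/+6 pattern tiles two-weekly visits exactly and appears to have been carried over to four-weekly ones. It should be corrected before the entire-administration-period database is locked.

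**What to change.** 1. Split the Study Windows table by Week 12 response status. Weeks 18 and 22, and the other rescue-only weeks, should apply to non-responders only.
2. Set each extension upper limit to target + 7. For responders this gives Week 16 = 106–120, Week 20 = 134–148, Week 24 = 162–176, and so on to Week 52 = 358–372. For non-responders it gives Week 28 = 190–204, and so on to Week 64 = 442–456. Within the split tables no windows overlap.
3. Add a sentence assigning any scheduled visit that still falls outside every window to its nominal visit.

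Steps 1 and 2 belong together. In the present single table, raising the limits alone would put Day 120 in both Weeks 16 and 18, and Day 148 in both Weeks 20 and 22. Closing Days 19–21 and 103–105 is not needed for compliant visits.

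The cost is a table edit, one added sentence and a programming parameter. Protocol 9.7 fixes the analysis plan before each database lock, so the change belongs in the SAP version finalised before the entire-administration-period lock.

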3.2 Planned Study Design

This is a multinational, multicenter, randomized, double-blind, placebo-controlled, parallel-group, early phase 2 clinical trial. This clinical trial consists of a screening period, remission-induction period (double blind), rescue period (open-label), extension period (open-label), post-observation period and follow-up period. Administration of the IMP is to start after confirming eligibility at baseline (at week 0 before the start of the IMP administration) upon having carried out the screening test within 42 days prior to the start of the IMP administration after obtaining consent.

Patients with moderate to severe active Crohn's disease are to be randomly allocated to an E6011 10mg/kg group and a placebo group (1:1) using stratified allocation in which race (Japanese/non-Japanese) and history of previous use of biologics (yes/no) are used as allocation factors. The administration volume (about 100 mL) is to be prepared based on the weight of the subject by diluting E6011 with a physiological saline solution and infused intravenously over approximately 30 minutes. The physiological saline solution used to dilute E6011 is to be used as a placebo. The remission-induction period is to last 12 weeks, with E6011 or placebo administered in a double-blind method on Week 0, Week 1, Week 2, and once every two subsequent weeks up to Week 10, and the efficacy of E6011 is to be evaluated in Week 12. Subjects with a reduction in the CDAI of 70 or more (responders) compared to baseline at evaluation on Week 12 are to move on to the open-label extension period. The extension

period is to last 40 weeks, with 10 mg/kg of E6011 administered every four weeks from Week 12 to Week 48 and E6011 efficacy is to be evaluated at Week 52.

[figure not shown]

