- i. Randomization is to be performed at baseline (before the start of IMP administration in Week 0).
- j. As many specified tests and evaluations as possible should be conducted for the assessment at discontinuation.
- k. E6011 to be administered after the transition to the rescue period or Extension period.
- l. PML onset is to be investigated over the phone, etc. at six months, one year, one and a half years, and two years after the final IMP dose.
- m. E6011 not to be administered when discontinuing at Week 24 for a lack of CDAI response.
- n. To be conducted during the Week 24 visit or 28 days after discontinuation only when discontinuing at Week 24 for a lack of CDAI response.
- o. The hematocrit value used to calculate the CDAI score at Week 0 or screening test (screening test value may also be used if this is within 7 days of the date of the CDAI assessment).

Table 2 Study Schedule (Responders)

Visit	Extension period (open-label)												Post-observation period	Follow-up period
	10	11	12	13	14	15	16	17	18	19	-	20	21	
Test/Observation Time	Week 16	Week 20	Week 24	Week 28	Week 32	Week 36	Week 40	Week 44	Week 48	Week 52	Discontinuation	28 days after completion/discontinuation	70 days after last dose administration	2 years after last dose administration ¹
Allowed deviations	± 7 days	± 7 days	± 7 days	± 7 days	± 7 days	± 7 days	± 7 days	± 7 days	± 7 days	± 7 days	-	± 7 days	+7 days	± 1 month
Signing of informed consent ^a														
Demographic characteristics, history of present illness														
Past medical history, complications														
Inclusion/exclusion criteria check														
Colonoscopy ^b												○	○	
IMP administration ^c	○	○	○	○	○	○	○	○	○					
Prior treatment and concomitant drugs/therapies	← →													
Physical findings	○	○	○	○	○	○	○	○	○	○	○	○		
Height/weight ^d	○	○	○	○	○	○	○	○	○	○	○	○		
Vital signs	○	○	○	○	○	○	○	○	○	○	○	○		
Standard 12-lead ECG			○		○							○	○	
Chest X-ray test														
Neurological symptoms ^e		○			○							○	○	
Anti-JCV antibody test												○	○	
Blood CD4 ⁺ cell test						○						○	○	
Viral test, tuberculosis test														
Pregnancy test ^f												○	○	
C. difficile toxin test														
CDAI, PRO2	○	○	○	○	○	○	○	○	○	○	○	○		
Haematology test, blood biochemistry test, urinalysis	○	○	○	○	○	○	○	○	○	○	○	○	○	
Adverse event	← →													(PML)
Serum E6011 concentration ^g ^h	○	○	○	○	○	○	○	○	○	○	○	○		
Serum anti-E6011 antibodies ^h	○	○	○	○	○	○	○	○	○	○	○	○		

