6.8.1 Primary Efficacy analysis

Primary analysis aims to determine if the treatment effect in CR100 response rate at Week 12 is expected to be higher for patients treated with E6011 than for patients treated with placebo.

The Bayesian posterior distribution of the difference in the CR100 rate at Week 12 between E6011 (p1) and placebo (p2) is obtained as p1-p2 posterior distributions. Non-informative prior (Jeffreys) Beta (1/2, 1/2) distributions described by (Oleksandr Sverdlov, Yevgen Ryeznik, & Sheng Wu, January 1, 2015) will be used to calculate p1 and p2 posterior distributions.

A MCMC algorithm will be performed using the following parameters:

- Number of chains = 3
- Initial values for the algorithm in every chain= 3 starting values simulated by a Beta (0.5, 0.5)
- Number of Burn-in = 100000

- Number of Iterations = 200000

Diagnostic for the MCMC convergence will be checked through the Geweke Diagnostics test, Raftery-Lewis Diagnostics, Gelman-Rubin convergence and the autocorrelation efficiency. In case of any issue due to an autocorrelation or non-convergence of the algorithm, the size of the burn-in, the number of iterations and a possible thinning will be evaluated.

Efficacy of E6011 will be confirmed if there was a 50% or more probability of the difference between both groups being 25% according to the posterior distribution.

Probability of the difference between groups being greater than zero will be also calculated.

Subjects with missing primary endpoint data due to premature discontinuation before 12 weeks after administration, or other reasons are treated as non-responders (NRI) in the modeling of the endpoint.

Primary analysis will be performed in the FAS population, and in the PPS population as a supportive analysis.

Two sensitivity analysis will be performed a Last Observation Carried Forward (LOCF) and an Observed Case (OC) imputation for CDAI at week 12 will be used instead of NRI.

Another supportive analysis will be performed following the same logistic regression model (randomization strata and treatment group as fixed factor) used in the secondary analysis.

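### The Week 12 window closes at Day 91 even if open-label E6011 has not started, so a late but still blinded Week 12 CDAI response can be scored as a primary non-response

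*SAP*

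**What the plan says.** SAP 6.6 assigns each assessment to an analysis week from a table of study days: "Week of evaluation for analysis will be defined in table 1 (similar approach as used in the E6011-J081-101 study"). The relevant rows (target, lower, upper) are "Week 12 85 78 91", "Week 14 99 96 102" and "Week 16 113 106 119". Between the first two, Week 13 has target Day 92, a blank lower bound and upper bound Day 95. No row depends on dosing.

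Protocol 9.5.2.1 sets the visit tolerance: "thereafter plus or minus 3 days of the scheduled dates up to Week 12". With the Week 12 target on Day 85, that is Days 82–88.

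SAP 6.8.1 gives the missing-data rule: "Subjects with missing primary endpoint data due to premature discontinuation before 12 weeks after administration, or other reasons are treated as non-responders (NRI"). Its two sensitivity analyses replace this with last observation carried forward (LOCF) or observed cases (OC).

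SAP 3.2 uses the Week 12 CDAI to route patients. "Subjects with a reduction in the CDAI of 70 or more (responders) compared to baseline at evaluation on Week 12" enter the extension; the others enter rescue. Footnote k of the schedule adds: "E6011 to be administered after the transition to the rescue period or Extension period". Footnote c puts dosing after that day's assessments.

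**The concern.** The Week 12 evaluation closes the blinded period: the patient is assessed, routed, and only then given open-label drug. A Week 12 CDAI taken late is therefore still blinded and free of open-label exposure. The table nevertheless stops at a calendar day and does not ask whether open-label dosing has begun.

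A patient who met CR100 at that evaluation could then be counted as a failure for the primary endpoint. The sensitivity analyses would not repair this. OC drops the patient. LOCF carries an earlier CDAI, normally Week 8, because CDAI is scheduled at Weeks 2, 4, 8 and 12. For a responder seen on Days 92–95, the value would carry a Week 13 label, a visit that the responder schedule does not contain.

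The decision rule is a threshold applied to 25 patients, so one reclassified patient can decide it.

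**Working it through.** **1. Where each study day falls.**

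| Study day | SAP 6.6 label | Within protocol ±3 days of Week 12 |
|---|---|---|
| 78–81 | Week 12 | no |
| 82–88 | Week 12 | yes |
| 89–91 | Week 12 | no |
| 92–95 | Week 13 | no |
| 96–102 | Week 14 | no |
| 103–105 | none | no |
| 106–119 | Week 16 | no |

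The SAP accepts visits up to 91 − 88 = 3 days beyond the tolerance. The affected visits start at Day 92, which is 92 − 88 = 4 days beyond it.

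**2. What happens to the patient.** Under SAP 5.1 a baseline CDAI and any later CDAI keep the patient in the FAS. With no value in Days 78–91, the non-responder rule applies. The score changes only if the patient met CR100.

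**3. The plan's own figure.** Inputs: Beta(1/2, 1/2) prior per arm (SAP 6.8.1); success if P(p1 − p2 ≥ 0.25) ≥ 0.50 (Protocol 9.7.1.6.1); 20 per arm and a true difference of 40% (SAP 8). The placebo rate is not given. Posteriors are independent Beta(x + 0.5, n − x + 0.5), and success is summed over all binomial outcomes. For placebo rates from 5% to 60% the probability of confirming efficacy is 0.807 to 0.874, which agrees with the stated figure of above 80%.

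**4. One patient at 25 enrolled.** Protocol 9.7.2 gives 25 in total; the split of 13 E6011 v 12 placebo is assumed.

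| E6011 | Placebo | P(difference ≥ 25%) | Verdict |
|---|---|---|---|
| 7/13 | 3/12 | 0.549 | confirmed |
| 6/13 | 3/12 | 0.386 | not confirmed |
| 6/13 | 2/12 | 0.562 | confirmed |

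From row 1 to row 2, losing one E6011 responder removes success. From row 2 to row 3, losing one placebo responder creates it. At true rates of 65% v 25%, the data lie where the first loss would matter in 13.5% of trials, and where the second would matter in 9.5%.

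**5. How often the verdict changes.** Let each Week 12 visit be this late, with no other CDAI in the window, with probability q, independently in both arms. Responders number X1 ~ Bin(13, 0.65) and X2 ~ Bin(12, 0.25). Of these, Bin(X1, q) and Bin(X2, q) are scored as failures. The verdict with all values counted is compared with the verdict after these losses. If C is the chance of any change and N the net loss of success probability, success is lost with probability (C + N)/2 and gained with probability (C − N)/2.

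| q (assumed) | Any late visit, 1 − (1 − q)^25 | Verdict changes (C) | Net loss (N) | Success lost | Success gained |
|---|---|---|---|---|---|
| 1% | 22% | 1.4% | 0.6 points | 1.0% | 0.4% |
| 2% | 40% | 2.6% | 1.3 points | about 2.0% | about 0.7% |
| 5% | 72% | 6.0% | 3.4 points | 4.7% | 1.3% |

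**6. Dependence on the placebo rate.** With q = 4%, 13 v 12 and a difference of 40%, the probability of success falls from 0.808 to 0.781, from 0.803 to 0.777 and from 0.806 to 0.780 at placebo rates of 10%, 20% and 30%. The net loss is 2.6 to 2.7 points throughout.

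**The case against.** A finite, prespecified window is ordinary practice, and this one is already wider than the protocol's. Only clear protocol deviations are affected, and the documents do not report any. The last blinded dose is scheduled for Week 10 (Day 71). A CDAI on Day 92 is then 92 − 71 = 21 days after it, against a planned 85 − 71 = 14. It can be argued that this is a different measurement from the planned endpoint. The blank lower bound for Week 13 may also mean that Week 13 was meant to start after the actual Week 12 visit.

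Much of this stands, and it limits the weight of the point. It does not remove the gap: however the blank is read, Week 12 still ends at Day 91. Lateness alone is a weak reason to score a measured, blinded response as a failure. The statement in SAP 4.5.1 that CDAI is used as entered in the eCRF settles the score, not the week to which it belongs.

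A reader might infer more than the documents support:

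- That the SAP calls an out-of-window CDAI missing. It does not say so; this follows from the table combined with the catch-all wording of the non-responder rule.
- That no analysis would use the value. SAP 6.8 also analyses efficacy over the entire administration period, where it could appear under a later label.
- That the value is fully on randomised treatment. It is blinded and before open-label drug, but longer after the last blinded dose than planned.
- That routing contradicts the primary endpoint. Routing uses a 70-point reduction and the endpoint 100 points, by design. The mismatch is only that a value counts as measured for one purpose and as missing for the other.

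**Conclusion.** The gap is real, and the effect is small. It needs a Week 12 evaluation on Day 92 or later, before open-label dosing, in a CR100 responder with no other CDAI in Days 78–91, and counts close to the decision boundary. On the assumptions in the working, the verdict changes in roughly 1 to 6 trials in 100. Most changes lose a success, but some create one, so the rule is not reliably conservative.

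It would be tempting to quote the 22%, 40% and 72% as the risk to the trial. Those are chances that any of 25 visits is late, not that the verdict changes. Likewise, 13.5% and 9.5% describe how often the data are pivotal, on the supposition that a responder is lost. The lateness rates, the 13/12 split and the true rates are all assumptions.

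**What to change.** Amend SAP 6.6 before the remission-induction data are unblinded:

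- Within Days 78–91, keep the closest-to-target rule.
- If there is no CDAI in Days 78–91, take as the Week 12 value the blinded Week 12 evaluation made before the first open-label infusion, up to a prespecified outer limit. The documents give no basis for a particular day, so the sponsor should choose and justify it.
- Let Week 13 and later labels take only assessments made after that infusion. This also settles the blank Week 13 bound.
- Report the fixed Day 78–91 window with non-responder imputation as a sensitivity analysis.

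The cost is one SAP rule and its programming; no trial procedure changes. The downside is that a few Week 12 values would be taken longer after the last blinded dose than planned, and values beyond the outer limit would still be imputed as failures. If no visit was this late, the result is unchanged.
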